### **7.10.4 Secondary Endpoints**

- Intravenous glucose infusion rate (GIR) [time frame: 0-30 mins induced hypoglycemia] (cumulative glucose infusion rate required to maintain insulin-induced hypoglycemia)
- Intravenous insulin infusion rate [time frame: 0-30 mins induced hypoglycemia] (cumulative insulin infusion rate required to maintain insulin-induced hypoglycemia)
- Change from Induction 1 (baseline visit) to Induction 2 (visit 7, Week 4) in other counter regulatory hormones (norepinephrine, glucagon, cortisol and growth hormone plasma concentrations) after 30 mins of induced hypoglycemia
- Change from Induction 1 (baseline visit) to Induction 2 (visit 7, Week 4) in Neuroglycopenic Symptom Scores (if hypoglycemia present) as documented using the hypoglycemia symptom questionnaire
- Change from Induction 1 (baseline visit) to Induction 2 (visit 7, Week 4) in Autonomic Symptom Scores (if hypoglycemia present) as documented using the hypoglycemia symptom questionnaire
- Change from baseline to Week 4 in CGM-derived hypoglycemia parameters of:
  - Proportional time spent with interstitial glucose <70, 60, and 50 mg/dL

- Rate of hypoglycemic event episodes at thresholds of plasma glucose <70, 60, and 50 mg/dL
- Area over the curve (AOC) of the reduction from baseline in the interstitial glucose from T0 to Tx, where x corresponds to time when interstitial glucose < 70, <60 and <50 mg/dL is achieved.
- Change from baseline to Week 4 in CGM-derived parameters of:
  - Average interstitial glucose and standard deviation
  - Proportional time within  $70 \leq \text{interstitial glucose} < 180$  mg/dL
  - Proportional time with  $\text{interstitial} \geq 180$  mg/dL
- Change from Induction 1 (baseline visit) to Induction 2 (visit 7, Week 4) in the Gold scale as a measure of hypoglycemia awareness

Pharmacodynamic endpoints (e.g., CGM derived parameters, counter regulatory hormones, GIR, insulin infusion rate) will be analyzed using a 1-factor (treatment) analysis of variance (ANOVA) model with treatment as the main effect.

The change from baseline for Gold scale, Neuroglycopenic Symptom Score, and Autonomic Symptom Score endpoints will be analyzed using non-parametric analysis of variance (Wilcoxon rank-sum test).

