## 2. SYNOPSIS

Protocol Number: XSGO-AF01	
Fixed Rate Continuous Subcutaneous Glucagon Infusion (CSGI) vs Placebo in Type 1 Diabetes Mellitus Patients with Recurrent Severe Hypoglycemia: Effects on Counter-Regulatory Responses to Insulin-Induced Hypoglycemia	
Principal Investigator:	Each participating clinical site will nominate a physician who, based on training and experience, will serve as principal investigator for that site. The Sponsor will qualify the Investigator.
IND:	120653
Project phase:	Phase 2a
Compound(s):	G-Pump™ (glucagon infusion)
Objectives:	
Primary Objective:
 
The change from baseline in plasma epinephrine will be compared between subjects who have received either 4 weeks of continuous subcutaneous glucagon infusion (CSGI) or placebo. After 30 minutes of a maintained insulin-induced hypoglycemia clamp (plasma glucose (PG) < 50 mg/dL), these hormone levels will be measured in adult type 1 diabetes (T1D) subjects with hypoglycemia associated autonomic failure (HAAF).
 
The secondary objectives are to:
 
 
1. Compare change from baseline in cumulative glucose infusion required to maintain glucose at 50 mg/dL for the first 30 minutes after the 50 mg/dL is achieved.
 
2. Compare changes from baseline in the other counter-regulatory hormones: norepinephrine, glucagon, cortisol and growth hormone.
 
3. Compare changes from baseline to week 4 in subject responses to a validated symptom questionnaire administered during induced hypoglycemia.
 
4. Compare changes from baseline to week 4 in continuous glucose meter (CGM)-derived hypoglycemia parameters of: 
 
a. Proportional time spent with interstitial glucose < 70, 60, and 50 mg/dL.
 
b. Rate of hypoglycemic event episodes at thresholds of < 70, 60, and 50 mg/dL.
 
 
 

5. Compare change from baseline to week 4 in CGM-derived parameters of:
  - a. Average glucose and proportional time:
    - i. Time within range with PG 70 - 180 mg/dL,
    - ii. Time above range with PG  $\geq$  180 mg/dL.
    - iii. Time below range < 70 mg/dL
  - b. Plasma glucose standard deviation.
6. Describe subject reported hypoglycemic events:
  - a. Symptomatic events confirmed with self-monitored glucose < 70 mg/dL.
  - b. Symptomatic events with no accompanying glucose meter reading or a reading  $\geq$  70 mg/dL.

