#### **5.3.2. Secondary Endpoints**

The secondary endpoints for this study include:

- intravenous glucose infusion rate (GIR).
- Other counter regulatory hormones norepinephrine, glucagon, cortisol and growth hormone plasma concentrations.
- Symptoms of hypoglycemia (if present) as documented using the hypoglycemia symptom questionnaire ([Appendix 1](#)).
- Various CGM derived variables (Secondary Objectives 4 & 5).
- Hypoglycemia awareness assessment by the Gold scale.
- Safety-related parameters including:
  - Reported hypoglycemic events..
  - Insulin dose.
  - Vital signs.
  - Physical exam.
  - ECG.
  - Plasma glucagon and serum glucagon antibodies.
  - Standard safety laboratory parameters.
  - Incidence of adverse events (AEs) and serious adverse events (SAEs).
  - Subjective injection site discomfort as reported by subjects using a 100-mm VAS and other questionnaires ([Appendix 3](#)).
  - Erythema and/or edema formation at site of injection assessed by an investigator using the modified Draize scale (see [Appendix 4](#)).

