## 3.2 Secondary Objectives

### 3.2.1 Efficacy Objectives

1. Compare change in cumulative glucose infusion to maintain glucose at 50 mg/dL for the first 30 minutes after the 50 mg/dL is achieved.
2. Compare change in cumulative insulin infusion to maintain glucose at 50 mg/dL for the first 30 minutes after the 50 mg/dL is achieved.
3. Compare changes in the other counter-regulatory hormones: norepinephrine, glucagon, cortisol and growth hormone.
4. Compare changes from Induction 1 (baseline visit) to Induction 2 (visit 7, week 4) in subject responses to a validated hypoglycemia symptom questionnaire administered during induced hypoglycemia.
5. Compare changes from baseline to week 4 in CGM-derived hypoglycemia parameters of:
  - a. Proportional time spent with interstitial glucose < 70, <60 and <50 mg/dL.
  - b. Rate of hypoglycemic event episodes at plasma glucose < 70, <60, and <50 mg/dL.
  - c. Area over the curve (AOC) of the reduction from baseline in the interstitial glucose from T0 (defined as the date/time of the CSGI injection) to Tx, where x corresponds to time when interstitial glucose < 70, <60 and <50 mg/dL is achieved.
6. Compare change from baseline to week 4 in CGM-derived parameters of:
  - a. Average (mean) interstitial glucose and standard deviation
  - b. proportional time with  $70 \leq$  interstitial glucose < 180 mg/dL,
  - c. proportional time with interstitial glucose  $\geq$  180 mg/dL.
7. Describe subject reported hypoglycemic events
  - a. Symptomatic events confirmed with self-monitored glucose < 70 mg/dL.
  - b. Symptomatic events with no accompanying glucose meter reading or a reading  $\geq$ 70 mg/dL.
  - c. Asymptomatic events of self-monitored glucose < 70 mg/dL.
  - d. Severe hypoglycemia as defined by affected consciousness of hypoglycemic origin confirmed by a glucose meter reading <50 mg/dL, requiring external assistance, or prompt recovery upon hypoglycemia treatment.
8. Describe change from Induction 1 (baseline visit) to Induction 2 (visit 7, week 4) of unawareness measured by the Gold scale.
9. Describe basal, bolus and total daily insulin dose changes by treatment group.
10. Describe the time course of the endpoints (primary and secondary 1-7) from week 4 through the rest of the study.
11. Describe non-serious and serious adverse events by treatment group.

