#### 4.2.1 Efficacy Endpoints

- Absolute change from Induction 1 (baseline visit) to Induction 2 (visit 7, Week 4) in plasma epinephrine concentration after 30 minutes of induced hypoglycemia with PG <50 mg/dL. The average of the non-missing results at each step will be used in analysis.
- Percent change from Induction 1 (baseline visit) to Induction 2 (visit 7, Week 4) in plasma epinephrine concentration after 30 minutes of induced hypoglycemia with PG <50 mg/dL by Diabetes Duration Category (<15 years, ≥15 years). The average of the non-missing results at each step will be used in analysis.
- Intravenous glucose infusion rate (GIR) [time frame: 0-30 mins induced hypoglycemia] (cumulative glucose infusion rate required to maintain insulin-induced hypoglycemia).
- Intravenous insulin infusion rate [time frame: 0-30 mins induced hypoglycemia] (cumulative insulin infusion rate required to maintain insulin-induced hypoglycemia).
- Change from Induction 1 (baseline visit) to Induction 2 (visit 7, Week 4) in other counter regulatory hormones (norepinephrine, glucagon, cortisol and growth hormone plasma concentrations) after 30 mins of induced hypoglycemia.
- Change from Induction 1 (baseline visit) to Induction 2 (visit 7, Week 4) in Neuroglycopenic Symptom Scores (if hypoglycemia present) as documented using the hypoglycemia symptom questionnaire.
- Change from Induction 1 (baseline visit) to Induction 2 (visit 7, Week 4) in Autonomic Symptom Scores (if hypoglycemia present) as documented using the hypoglycemia symptom questionnaire.
- Change from baseline to Week 4 in CGM-derived hypoglycemia parameters of:
  - Proportional time spent with interstitial glucose (IG) <70, 60, and 50 mg/dL;
  - Rate of hypoglycemic event episodes at thresholds of plasma glucose <70, 60, and 50 mg/dL.
  - Area over the curve (AOC) of the reduction from baseline in the interstitial glucose from T0 (defined as the date/time of the CSGI injection) to Tx, where x corresponds to time when interstitial glucose < 70, <60 and <50 mg/dL is achieved.
- Change from baseline to Week 4 in CGM-derived parameters of:
  - Average interstitial glucose and standard deviation;
  - Proportional time within  $70 \leq \text{interstitial glucose} < 180$  mg/dL;

- Proportional time with interstitial glucose  $\geq 180$  mg/dL.
- Change from Induction 1 (baseline visit) to Induction 2 (visit 7, Week 4) in the Gold scale as a measure of hypoglycemia awareness.

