14.2.2.1.2*	Absolute change from Induction 1 (Baseline visit) to Induction 2 (Visit 7, Week 4) in Plasma Epinephrine Concentration During Induced Hypoglycemia with PG <50 mg/dl Per Protocol Population	14.2.1.1
14.2.2.2.1*	Percent change from Induction 1 (Baseline visit) to Induction 2 (Visit 7, Week 4) in Plasma Epinephrine Concentration During Induced Hypoglycemia with PG <50 mg/dl by Duration of Diabetes Category Intent-to-Treat Population	14.2.1.1
14.2.2.2.2*	Percent change from Induction 1 (Baseline visit) to Induction 2 (Visit 7, Week 4) in Plasma Epinephrine Concentration During Induced Hypoglycemia with PG <50 mg/dl by Duration of Diabetes Category Per Protocol Population	14.2.1.1
14.2.2.3.1*	Change from Induction 1 (Baseline visit) in Counter Regulatory Hormones During Induced Hypoglycemia with PG <50 mg/dl - Intent-to-Treat Population	
14.2.2.3.2*	Change from Induction 1 (Baseline visit) in Counter Regulatory Hormones During Induced Hypoglycemia with PG <50 mg/dl - Per Protocol Population	14.2.2.3.1
14.2.2.4.1*	Change from Induction 1 (Baseline visit) in Counter Regulatory Hormones During Induced Hypoglycemia with PG <50 mg/dl – ANOVA - Intent-to-Treat Population	
14.2.2.4.2*	Change from Induction 1 (Baseline visit) in Counter Regulatory Hormones During Induced Hypoglycemia with PG <50 mg/dl – ANOVA - Per Protocol Population	14.2.2.4.1
14.2.2.5.1	Summary of Cumulative Glucose Infusion Rate (GIR) Required to Maintain Insulin-Induced Hypoglycemia Intent-to-Treat Population	
14.2.2.5.2	Summary of Cumulative Glucose Infusion Rate (GIR) Required to Maintain Insulin-Induced Hypoglycemia Per Protocol Population	14.2.2.5.1
14.2.2.6.1	Summary of Cumulative Insulin Infusion Rate Required to Maintain Insulin-Induced Hypoglycemia Intent-to-Treat Population	14.2.2.5.1
14.2.2.6.2	Summary of Cumulative Insulin Infusion Rate Required to Maintain Insulin-Induced Hypoglycemia Per Protocol Population	14.2.2.5.1
14.2.2.7.1.1	Change from Induction 1 (Baseline visit) in Average Neuroglycopenic Scores (ANS), Average Autonomic Scores (AAS) and Average Total Scores (ATS) with PG <70 mg/dl Intent-to-Treat Population	
14.2.2.7.1.2	Change from Induction 1 (Baseline visit) in Average Neuroglycopenic Scores (ANS), Average Autonomic	14.2.2.7.1.1

Table Number	Table Title	Shell Number (if repeat)
	Scores (AAS) and Average Total Scores (ATS) with PG <70 mg/dl Per Protocol Population	

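### The objective for glucose infusion is a change from baseline, but the SAP endpoint names no Induction 1 reference and its ANOVA has no baseline term; cumulative insulin infusion has the same gap

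*SAP*

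**What the plan says.** **Objective.** The protocol synopsis, secondary objective 1, reads "Compare change from baseline in cumulative glucose infusion required to maintain glucose at 50 mg/dL for the first 30 minutes". SAP 3.2.1, objective 1, reads "Compare change in cumulative glucose infusion to maintain glucose at 50 mg/dL for the first 30 minutes", and Protocol 5.2 is worded the same way. SAP 3.2.1, objective 2, sets a parallel change comparison for cumulative insulin infusion.

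**Endpoint.** Protocol 5.3.2 lists only "intravenous glucose infusion rate (GIR" and mentions no change. SAP 4.2.1 and 7.10.4 give "Intravenous glucose infusion rate (GIR) [time frame: 0-30 mins induced hypoglycemia] (cumulative glucose infusion rate required to maintain insulin-induced hypoglycemia". The insulin infusion endpoint is built the same way. In those two SAP lists, the hormone, symptom-score, CGM and Gold scale endpoints are all expressed as a change from Induction 1 or from baseline; the two infusion endpoints are not.

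**Model.** Protocol 11.2.2 plans a mixed model for cumulative glucose infusion, the other hormones and the CGM variables. SAP 7.10.4 replaces it with a one-factor ANOVA whose only term is treatment, covering CGM parameters, hormones, GIR and insulin infusion rate. SAP section 10, which lists changes from the protocol analysis, mentions neither this switch nor any redefinition of the glucose infusion endpoint.

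**Status.** SAP 7.10.5 treats all secondary endpoints as descriptive, without multiplicity control.

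**The concern.** The objective and the endpoint describe different quantities, and nothing between them reconciles the two. SAP 7.2 has derivation rules for hormones, CGM parameters and questionnaires but none for the infusion endpoints. Inductions take place at Visits 3, 7, 9 and 11, and the ANOVA sentence does not say which one supplies the value. Two programmers working from this SAP could reasonably analyse different variables.

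Precision is also at stake. Each subject has an Induction 1 infusion record under the same clamp procedure. A treatment-only model on a Week 4 value discards it, in a trial with 16 subjects per arm.

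**Working it through.** **1. Text comparison for glucose infusion.**

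| Place | Change stated? |
|---|---|
| Protocol synopsis, objective 1 | Yes, from baseline |
| Protocol 5.2, objective 1 | Yes |
| SAP 3.2.1, objective 1 | Yes |
| Protocol 5.3.2, endpoint | No |
| SAP 4.2.1, endpoint | No |
| SAP 7.10.4, endpoint | No |
| SAP 7.10.4, model | Not stated; no baseline term, no visit term, no induction named |
| SAP section 10 | Difference not listed |

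For insulin infusion, SAP 3.2.1 objective 2 states a change and SAP 4.2.1 and 7.10.4 do not.

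**2. The plan's own figure.** The documents give no power, SD or correlation for glucose infusion. The only sample size is for epinephrine: difference 1.5 nmol/l, SD 1.34 nmol/l, 80% power, alpha 5%. A two-sided two-sample t-test gives 13.56, so 14 per group, and 3 × 14 = 42, which matches the synopsis. At 16 per group that calculation gives 86.5% power. This fixes the test convention used below and says nothing about glucose infusion.

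**3. Chance imbalance at Induction 1.** In units of the between-subject SD, the standard error of the between-arm difference is √(1/16 + 1/16) = 0.35 for 16 v 16 and √(1/16 + 1/32) = 0.31 for the combined comparison. An unadjusted Week 4 analysis makes no use of this measured difference.

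**4. Precision of the three analyses.** Assume equal SDs (set to 1) at both inductions and correlation ρ between them. Then:
- level: SD = 1
- unadjusted change: SD = √(2(1 − ρ))
- adjusted for the Induction 1 value: SD = √(1 − ρ²)

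With 16 v 16, two-sided 5%, the standardised difference with 80% power is 1.024. For each ρ, take the effect with 80% power on unadjusted change, δ = 1.024 × √(2(1 − ρ)), and recompute power from the noncentral t with the other two SDs. The one degree of freedom used by the covariate is ignored.

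| ρ | SD of change | δ | Power, change | Power, level | Power, adjusted |
|---|---|---|---|---|---|
| 0.3 | 1.18 | 1.21 | 80% | 91% | 94% |
| 0.5 | 1.00 | 1.02 | 80% | 80% | 90% |
| 0.6 | 0.89 | 0.92 | 80% | 71% | 88% |
| 0.7 | 0.77 | 0.79 | 80% | 58% | 86% |
| 0.8 | 0.63 | 0.65 | 80% | 43% | 84% |

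Level and unadjusted change are equal at ρ = 0.5, and level is better below it. The adjusted analysis beats both at every ρ shown.

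**The case against.** The strongest reply is that this is a wording gap, and that a reader might wrongly infer from it that the ANOVA is definitely run on a raw level and that objective 1 is therefore not tested. The documents do not establish that. The model sentence in SAP 7.10.4 says neither level nor change, and it names GIR alongside hormones and CGM parameters that are defined as changes. The table title "Summary of Cumulative Glucose Infusion Rate (GIR) Required to Maintain Insulin-Induced Hypoglycemia Intent-to-Treat Population" does not settle it either: SAP 7.11.2 and 7.11.3 require changes from baseline for laboratory data and vital signs, yet Tables 14.3.4.1.1 and 14.3.6.1 are also titled as summaries. The shells are not in the documents, and SAP 7.3.2 presents baseline and each visit where applicable. This part of the reply stands.

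A second tempting reading is that a level analysis would mistake baseline imbalance for a treatment effect. Under randomisation a Week 4 comparison is unbiased, and chance imbalance is already reflected in its standard error. What is lost is precision.

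Third, ρ is unknown and glucose infusion was never powered, so no power loss against unadjusted change can be demonstrated. That stands too, and the table in the working is only an illustration. It does not remove the case for adjustment, which comes out ahead across the whole range shown.

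Importance should not be overstated. The endpoint is descriptive, third in the SAP 4.2.1 list, and its tables are not marked for the primary endpoint analysis. Scaling to body weight is a matter of preference and no part of this point.

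What the reply does not answer is that the SAP leaves the variable, the induction and the baseline handling unspecified for an objective that asks for a change.

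**Conclusion.** The point holds as a mismatch and an under-specification. Three objective statements call for a change in cumulative glucose infusion. The SAP endpoint omits it in both places, the model has no baseline term and names no induction, and section 10 is silent on this and on the move from a mixed model to ANOVA. Cumulative insulin infusion has the same gap between objective and endpoint.

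The consequence is modest. There is no bias and no effect on the primary endpoint or its alpha. In the illustration, adjustment gives 84% to 94% power, against 43% to 91% for the level and 80% for unadjusted change. Those figures assume equal SDs at the two inductions, ρ between 0.3 and 0.8, 16 v 16 and a two-sided 5% test. The ranking in favour of adjustment does not depend on which ρ in that range is true; the size of the gain does.

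**What to change.** - In SAP 4.2.1 and 7.10.4, define both infusion endpoints as the change from Induction 1 to Induction 2 in the cumulative amount infused over the 0-30 minute window.
- Analyse each with treatment and the Induction 1 value as covariate. With that covariate in the model, the treatment estimate is the same whether the response is the change or the Week 4 value, so the objective is met without giving up precision if ρ is low.
- Align Tables 14.2.2.5.x and 14.2.2.6.x with this definition.
- Record in SAP section 10 the move away from the protocol's mixed model.

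The cost is SAP wording, one derivation and one covariate. The induction procedure is already run at baseline and Week 4, so no new data are needed.

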### **11.2.2. Pharmacodynamic Secondary Endpoints:**

The secondary endpoints cumulative glucose infusion to maintain glucose at 50 mg/dl for the first 30 minutes, other counter regulatory hormones, and CGM derived variables will be analyzed by mixed model analysis.

Other endpoints will be analyzed descriptive with inferential testing being performed should the descriptive data indicate differences of clinical importance between the groups.

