## 2 INTRODUCTION

This document describes the planned data analyses for clinical trial XSGO-AF01 sponsored by Xeris Pharmaceuticals, Inc.

This SAP should be read in conjunction with the amended version of study protocol (XSGO-AF01, Version 4.0, dated 21-Dec 2018). Any further changes to the protocol or eCRF may necessitate updates to the SAP.

This SAP supersedes the statistical considerations identified in the protocol; where considerations are substantially different these differences will be identified. If additional analyses are required to supplement objectives described in the SAP, they may be performed and will be identified in the Clinical Study Report (CSR).

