### **6 RANDOMIZATION**

The randomization scheme is 1:1:1 for high dose, low dose and placebo. Each group will have 16 subjects, but the placebo group will be matched to high and low infusion rates (8 in each group). The randomization is stratified by site.

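### SAP 7.10.4 replaces the protocol's mixed model for pharmacodynamic secondary endpoints with a treatment-only ANOVA, does not declare the change, and adjusts for neither baseline nor site

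*SAP*

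**What the plan says.** Protocol 11.2.2 starts its list with cumulative glucose infusion and continues: "other counter regulatory hormones, and CGM derived variables will be analyzed by mixed model analysis". It names no covariate, visit term or covariance structure.

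SAP 7.10.4 covers CGM parameters, counter-regulatory hormones and glucose infusion, and adds the insulin infusion rate. It says that these "will be analyzed using a 1-factor (treatment) analysis of variance (ANOVA) model with treatment as the main effect". The table list in SAP 12 plans matching ANOVA tables for the hormones (14.2.2.4.1 and 14.2.2.4.2), both marked for the primary endpoint analysis.

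On the form of the outcome, the hormone bullet in SAP 7.10.4 is a change from Induction 1 to Induction 2 "in other counter regulatory hormones (norepinephrine, glucagon, cortisol and growth hormone plasma concentrations) after 30 mins of induced hypoglycemia". The glucose and insulin infusion bullets there do not mention change. The objective in SAP 3.2.1 does: "Compare change in cumulative glucose infusion to maintain glucose at 50 mg/dL for the first 30 minutes".

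On design, SAP 6 states: "The randomization is stratified by site". On departures from the protocol, SAP 2 states that "where considerations are substantially different these differences will be identified". SAP 10 lists five changes, and none concerns the model for secondary endpoints. SAP 7.10.5 treats all secondary endpoints as descriptive, without multiplicity adjustment.

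**The concern.** There are two separate issues.

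The first is disclosure. The SAP may depart from the protocol, since both documents give it precedence, but it undertakes to say where it does so substantially. Changing the model for three endpoint families is substantial, and a reader who relies on SAP 10 would not learn of it. The hormone tables also belong to the analysis that is unblinded at group level before final database lock, so the model used there is the first one anyone will see.

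The second is precision. The trial measures each of these quantities at baseline and randomises within site, yet the model uses neither as a term. With 16 subjects per arm, the estimates and intervals for hormones, glucose infusion and CGM hypoglycaemia are the main supporting evidence. Subtracting baseline without also fitting it as a covariate gives wider intervals than the same data allow, and leaves a chance baseline imbalance only partly handled. For the weekly CGM endpoints, separate one-factor comparisons also leave a subject with no Week 4 record out of that week's comparison even when Weeks 1 to 3 are present. SAP 7.10 gives no missing-data rule for secondary endpoints.

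**Working it through.** **The plan's own figure.** The documents give no power or precision figure for these endpoints. The only one is for the primary endpoint: difference 1.5 nmol/l, SD 1.34 nmol/l, 80% power, alpha 5%, N = 42 (protocol synopsis). The standardised difference is 1.5/1.34 = 1.12. A two-sided two-sample t-test (noncentral t) needs 13.56, so 14 per arm, and 3 × 14 = 42. The 48 randomised allow for 1 − 42/48 = 12.5% attrition. The figure reproduces, and nothing below depends on it.

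**The switch, side by side.** Protocol 11.2.2: these endpoints "will be analyzed by mixed model analysis". SAP 7.10.4: one-factor ANOVA, treatment only. SAP 10: five entries (primary endpoint to percent change, absolute change moved to secondary, analysis by diabetes duration, the severe hypoglycaemia threshold, the per-protocol definition). The model change is absent.

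**Baseline adjustment.**

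- Inputs: 16 per arm (SAP 6). The correlation ρ between baseline and week 4 is not in the documents, so 0.3 to 0.9 is assumed. The variance σ² is assumed equal at both visits.
- Variance of a change score: 2(1 − ρ)σ².
- Residual variance after ANCOVA on baseline: (1 − ρ²)σ².
- Ratio, ANCOVA to change score: (1 − ρ²) / [2(1 − ρ)] = (1 + ρ)/2.

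The power column takes an effect with exactly 80% power under one-factor ANOVA on change (16 per arm, 45 residual df). That effect is 1.01 SD of the change. Power is then recomputed with the reduced variance, 44 df and a factor of 1 + 1/43 for estimating the covariate slope.

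| ρ (assumed) | ANCOVA / change variance | Variance cut | Change-score interval relative to ANCOVA | Power with baseline adjustment |
|---|---|---|---|---|
| 0.3 | 0.65 | 35% | 1.24 | 93% |
| 0.5 | 0.75 | 25% | 1.15 | 89% |
| 0.7 | 0.85 | 15% | 1.08 | 85% |
| 0.9 | 0.95 | 5% | 1.03 | 81% |

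The interval column is the square root of 2/(1 + ρ). At ρ = 0.5 the gain equals 1/0.75 = 1.33, or about a third more subjects.

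**If glucose and insulin infusion are analysed as raw week-4 values.** The ratio above does not apply. The comparison becomes (1 − ρ²)σ² against σ², a cut of ρ²: 9%, 25%, 49% and 81% at the same four correlations.

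**Site.** Inputs: 6 to 8 sites (protocol synopsis). The intraclass correlation (ICC) is not in the documents. With residual variance multiplied by (1 − ICC) and df reduced by (sites − 1), the same 80% effect has power of about 80% at ICC 0 (no gain), 82% at 0.05, 84% at 0.10 and 88% at 0.20.

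**The case against.** The strongest reply is that this is an efficiency choice, not an error. A change score already subtracts baseline, the comparison is unbiased under randomisation, the SAP is entitled to override the protocol, and the endpoints are descriptive. All of that stands, and it limits the weight of the point. It does not answer the missing entry in SAP 10.

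Several stronger readings are tempting, and the documents do not support them:

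- **That the SAP removed baseline and site terms which the protocol had specified.** Protocol 11.2.2 names no terms. The precision loss is therefore measured against a baseline-adjusted model, not against the protocol's own, and there is no specified model to restore.
- **That every pharmacodynamic endpoint suffers the tabulated loss.** The infusion bullets in SAP 7.10.4 do not mention change. The area-over-the-curve endpoint (SAP 7.2.10) accumulates reductions from one pre-dose reading up to a threshold crossing, so the two-visit formula does not fit it. The insulin infusion rate was added by the SAP, and protocol 9.4.1 holds it constant unless insufficient. Times below low thresholds and episode counts may be skewed, so the normal-theory ratio is only a guide there.
- **That repeated measures are lost throughout.** Hormones and glucose infusion have one post-baseline induction at the end of treatment. The later two fall months after treatment stops, and the SAP objectives only describe that time course. A repeated-measures model would add little for the week-4 contrast, and ANCOVA also needs both values. The point applies to the weekly CGM endpoints.
- **That omitting site certainly costs precision.** With 48 subjects over 6 to 8 sites there are only 6 to 8 per site, about two or three per arm, and the gain may be nil.

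**Conclusion.** The point holds in two parts. The undeclared change of model follows from the text alone and needs no assumption. The precision gain is real but conditional. For endpoints analysed as change between two visits with equal variances, baseline adjustment cuts the variance by 35% at ρ = 0.3, falling to 5% at ρ = 0.9. The documents give neither ρ nor the site ICC, so no single figure can be claimed, and the site contribution runs from nothing upwards.

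A reader might infer that the SAP analysis is biased or that the trial's main conclusion is at risk. Neither follows. The ANOVA is valid under randomisation, the primary test and sample size are untouched, and the secondary endpoints stay descriptive. This is a change that should be made because it is nearly free, not because the plan fails without it.

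**What to change.** 1. In SAP 7.10.4, analyse the hormone, glucose infusion and insulin infusion endpoints at week 4 by ANCOVA with treatment and the baseline value, and site as a pooled or random factor because sites are small. With baseline in the model, the treatment estimate is the same whether the outcome is the week-4 value or the change, so the ambiguity in the infusion bullets no longer matters.
2. For the weekly CGM endpoints other than area over the curve, use a repeated-measures mixed model with treatment, week, treatment-by-week and baseline. State the covariance structure.
3. List the departure from the protocol's mixed model in SAP 10. If the sponsor prefers to keep the one-factor ANOVA, declare it there with a reason.

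The cost is SAP wording, standard code and revised table shells, with no new data or visits. Because the hormone tables are part of the primary endpoint analysis, the amendment should be signed before that analysis is unblinded at group level.
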